Appendix E: Criteria for Threshold Analysis

Table 11-2 Threshold Analysis Criteria for Laboratory Tests (as applicable)

Parameter	Threshold Analysis	Comments
Clinical Chemistry (LFT)		
ALT	>ULN - ≤3xULN >3x - ≤5xULN >5x - ≤8xULN >8x - ≤20.0xULN >20.0xULN	FDA DILI Guidance Jul 2009.
AST	>ULN - ≤3xULN >3x - ≤5xULN >5x - ≤8xULN >8x - ≤20.0xULN >20.0xULN	FDA DILI Guidance Jul 2009.
ALT or AST	(ALT>ULN - ≤ 3xULN) or (AST>ULN - ≤3xULN) (ALT>3x - ≤5xULN) or (AST>3x - ≤5xULN) (ALT>5x - ≤8xULN) or (AST>5x - ≤8xULN) (ALT>8x - ≤20xULN) or (AST>8x - ≤20xULN) ALT>20xULN or AST>20xULN	FDA DILI Guidance
Alkaline Phosphatase	>ULN - ≤1.5xULN >1.5 - ≤2.5xULN >2.5 - ≤5.0xULN >5.0 - ≤20.0xULN >20.0xULN	FDA DILI Guidance Jul 2009.
Total Bilirubin	>ULN - ≤1.5xULN >1.5 - ≤2xULN >2 - ≤3xULN >3 - ≤10xULN >10xULN	FDA DILI Guidance Jul 2009.
Direct Bilirubin	>ULN - ≤1.5xULN >1.5 - ≤2xULN >2 - ≤3xULN >3 - ≤10xULN >10xULN	FDA DILI Guidance Jul 2009.
Indirect Bilirubin	>ULN - ≤1.5xULN >1.5 - ≤2xULN >2 - ≤3xULN >3 - ≤10xULN >10xULN	FDA DILI Guidance Jul 2009.
ALT and Total Bilirubin	ALT>3xULN and TBILI>2xULN	FDA DILI Guidance Jul 2009.

Table 11-2 Threshold Analysis Criteria for Laboratory Tests (as applicable)

Parameter	Threshold Analysis	Comments
AST and Total Bilirubin	AST>3xULN and TBILI>2xULN	FDA DILI Guidance Jul 2009.
(ALT or AST) and Total Bilirubin	(ALT>3xULN or AST>3xULN) and TBILI>2xULN	and FDA DILI Guidance Jul 2009.
GGT	>ULN - ≤2.5xULN >2.5 - ≤5.0xULN >5.0 - ≤20.0xULN >20.0xULN	CTCAE grade 1-4
Clinical Chemistry (NON-LFT)		
Albumin	<LLN - ≥30 g/L <30 - ≥20 g/L <20 g/L	CTCAE grade 1-3
Amylase	>1x - ≤1.5xULN >1.5x - ≤2xULN >2x - ≤5xULN >5xULN	Criteria based upon CTCAE
Creatinine	>ULN - ≤1.5xULN >1.5 - ≤3.0xULN >3.0 - ≤6.0xULN >6.0xULN	CTCAE grades 1-4
Lipase	>ULN - ≤1.5xULN >1.5x - ≤2xULN >2x - ≤5xULN >5xULN	Criteria based upon CTCAE
Total protein	<LLN >ULN	No CTCAE
Creatine kinase	>ULN - ≤2.5xULN >2.5 - ≤5xULN >5 - ≤10xULN >10xULN	CTCAE grades 1-4
Hematology		
Hemoglobin	Hgb decreased (anemia) <LLN - ≥100 g/L <100 - ≥80 g/L <80 g/L Hgb increased >ULN - ≤20 g/L above ULN >20 g/L above ULN - ≤40 g/L above ULN >40 g/L above ULN	CTCAE grade 1-3 CTCAE grade 1-3
Platelets	Platelet decreased <LLN - ≥75.0 x 10e9 /L <75.0 - ≥50.0 x 10e9 /L <50.0 - ≥25.0 x 10e9 /L <25.0 x 10e9 /L	CTCAE grade 1-4

Table 11-2 Threshold Analysis Criteria for Laboratory Tests (as applicable)

Parameter	Threshold Analysis	Comments
	Platelet increased >ULN	No CTCAE available
Reticulocytes/Erythrocytes (%)	<LLN >ULN	No CTCAE
Coagulation		
Activated partial thromboplastin time (PTT)	>ULN - ≤1.5xULN >1.5 - ≤2.5xULN >2.5xULN	CTCAE grade 1-3
Prothrombin time (PT) International Normalized Ratio (INR)	>ULN - ≤1.5xULN >1.5 - ≤2.5xULN >2.5 x ULN	CTCAE grade 1-3

Table 11-3 Threshold Analysis Criteria for ECGs

Parameter	Threshold Analysis	Comments
HR	Bradycardia ≤50 bpm Tachycardia ≥140 bpm	
PR	≥220 ms and increase from baseline ≥20 ms	
QRS	≥120 ms	
QTc	Absolute values (ms) >450 ms (Male); >470 ms (Female) ≥500 ms Increase from baseline Increase from baseline 30-60 ms Increase from baseline >60 ms	To be applied to any kind of QT correction formula.

Table 11-4 Threshold Analysis Criteria for Vital Signs

Parameter	Threshold Analysis	Comments
SBP	>120 mmHg <70 mmHg	
DBP	>80 mmHg <50 mmHg	

Appendix F: Adverse Events of Special Interest

Table 11.6 MedDRA Preferred Terms for Event of Special Interest

Adverse event of special interest	MedDRA preferred terms
Elevated transaminases	Alanine aminotransferase abnormal, Alanine aminotransferase increased, Aspartate aminotransferase abnormal, Aspartate aminotransferase increased, Transaminases abnormal, Transaminases increased, Liver function test abnormal, Liver function test increased, Hypertransaminasaemia, Hepatic enzyme abnormal, Hepatic enzyme increased
Rash	Rash, Rash erythematous, Rash macular, Rash maculo-papular, Rash maculovesicular, Rash vesicular, Rash pruritic, Rash follicular, Rash pustular, Nodular rash, Drug eruption, Fixed eruption, Urticaria, Urticaria papular, Urticaria vesiculosa, Urticular dermatitis, Rash morbilliform, Rash papular, Rash papulosquamous, Rash rubelliform, Rash scarlatiniform, Drug hypersensitivity, Type IV hypersensitivity reaction, Dermatitis, Dermatitis atopic, Epidermolysis, Skin toxicity, Dermatitis allergic, Dermatitis exfoliative, Dermatitis exfoliative generalised, Erythema multiforme, Exfoliative rash, Mucocutaneous rash, Acute generalised exanthematous pustulosis, Cutaneous vasculitis, Urticular vasculitis, Dermatitis bullous, Drug reaction with eosinophilia and systemic symptoms, Epidermal necrosis, Oculomucocutaneous syndrome, Skin exfoliation, Skin necrosis, Stevens-Johnson syndrome, Toxic epidermal necrolysis, Toxic skin eruption, Perioral dermatitis, Vasculitic rash, Immune-mediated dermatitis, SJS-TEN overlap, Erythrodermic atopic dermatitis, Scrotal dermatitis, Anal rash

Note: the preferred terms listed in the table is based on the MedDRA version applicable at the time of finalization of the SAP. If the MedDRA version is upgraded at the time of the analysis, the corresponding preferred terms based on the upgraded version, including adding, removing and renaming the preferred terms, will be used in the analysis of adverse events of special interest.

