13.1.1.2 Clinically Significant Assessments

Study assessments including laboratory tests, ECGs, PEs, and vital signs will be assessed and those deemed to have clinically significant worsening from baseline will be documented as an AE. When possible, a clinical diagnosis for the study assessment will be provided, rather than the abnormal test result alone (e.g., urinary tract infection, anemia). In the absence of a diagnosis, the abnormal study assessment itself will be listed as the AE (e.g., bacteria in urine or decreased hemoglobin).

An abnormal study assessment is considered clinically significant if the subject has 1 or more of the following:

- Concomitant signs or symptoms related to the abnormal study assessment
- Further diagnostic testing or medical/surgical intervention
- A change in the dose of study drug or discontinuation from the study

Repeat testing to determine whether the result is abnormal, in the absence of any of the above criteria, does not necessarily meet clinically significant criteria. The determination of whether the study assessment results are clinically significant will be made by the investigator.

A laboratory value that is Grade 4 will not automatically be an SAE. A Grade 4 laboratory value will be an SAE if the subject's clinical status indicates a life-threatening AE.

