13.1.1.3 Documentation of Adverse Events

All AEs will be collected from the time the ICF is signed until the following times:

- For subjects who do not enroll: until time of screen failure (e.g., screen failure, withdrawal of consent)

- For enrolled subjects who have a Safety Follow-up Visit: through the Safety Follow-up Visit
- For enrolled subjects who do not have a Safety Follow-up Visit, the earliest of
 - o 28 days after the last dose of study drug, or
 - o the ETT Visit, if that visit is 3 weeks or later following the last dose of study drug (see Section 9.1.3)

All subjects' parents or legal guardians will be queried, using nonleading questions, about the occurrence of AEs at each study visit. When possible, a constellation of signs and/or symptoms will be identified as 1 overall event or diagnosis. All AEs for enrolled subjects will be recorded in the CRF and source document. AEs for subjects who are screened but not subsequently enrolled will be recorded only in the subject's source documents. The following data will be documented for each AE:

- Description of the event
- Classification of "serious" or "nonserious"
- Date of first occurrence and date of resolution (if applicable)
- Severity
- Causal relationship to study drug(s)
- Action taken
- Outcome
- Concomitant medication or other treatment given

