8.4.1.1 Adverse Events of Special Interest

For this study, elevated transaminases events and rash events, as determined by MedDRA PTs in [Appendix F](#), are considered as AESIs.

For treatment-emergent elevated transaminases events and rash events, the following categories will be summarized overall:

- Subjects with events
- Subjects with events by maximum severity
- Subjects with events leading to treatment discontinuation
- Subjects with events leading to treatment interruption

- Subjects with serious events
- Subjects with related serious events
- Subjects with events leading to death
- Duration of events
- Time-to-onset of first event (with the first dose date of TC in the OLE as the reference while calculating time-to-onset)

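### The 'elevated transaminases' AESI counts only laboratory-finding terms, so events recorded only as a hepatic-injury diagnosis, as the protocol prefers, would be missing from the AESI summary

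*SAP*

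**What the plan says.** SAP 8.4.1.1 names two AESIs: "elevated transaminases events and rash events, as determined by MedDRA PTs in" Appendix F. It gives no laboratory-value criterion and no wider hepatic grouping.

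For elevated transaminases, Appendix F lists "Alanine aminotransferase abnormal, Alanine aminotransferase increased, Aspartate aminotransferase abnormal, Aspartate aminotransferase increased, Transaminases abnormal, Transaminases increased", followed by "Liver function test abnormal, Liver function test increased, Hypertransaminasaemia, Hepatic enzyme abnormal, Hepatic enzyme increased". The note under the table lets the list change only through a MedDRA version upgrade.

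Protocol 13.1.1.2 sets the recording rule for abnormal assessments: "When possible, a clinical diagnosis for the study assessment will be provided, rather than the abnormal test result alone". It also has a fallback: "In the absence of a diagnosis, the abnormal study assessment itself will be listed as the AE". Protocol 13.1.1.3 adds a merging rule: "When possible, a constellation of signs and/or symptoms will be identified as 1 overall event or diagnosis".

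The rash list in the same Appendix F table is built differently. It contains named diagnoses as well as descriptions of a finding, for example "Stevens-Johnson syndrome, Toxic epidermal necrolysis".

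**The concern.** The SAP list and the protocol's recording rule pull in opposite directions. A site that follows the protocol and records only drug-induced liver injury, say, produces an event that no term in Appendix F matches.

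The loss could be selective. Protocol 9.8.1 requires the cause to be investigated once an interruption threshold is met, and one of those thresholds combines raised enzymes with raised bilirubin or jaundice. Investigation makes a diagnosis more likely, and several concurrent signs invite a single overall diagnosis. A mild rise that is not worked up stays under a laboratory term and is counted.

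Elevated transaminases is one of only two AESIs under the primary safety objective. Its summary in SAP 8.4.1.1 covers maximum severity, seriousness, related seriousness, interruption, discontinuation, death, duration and time to onset. Duration and time to onset are summarised nowhere else in the SAP.

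**Working it through.** The documents give no event rate, power or precision figure for this point, so there is no plan figure to reproduce. The check counts the terms, traces how a case would be recorded and counted, and then gives an illustration on stated assumptions.

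**1. Term count (SAP Appendix F).**
- Elevated transaminases: 6 + 5 = 11 terms. Ten end in 'abnormal' or 'increased'. The other, hypertransaminasaemia, also only names the raised enzyme. Hepatic diagnoses: 0 of 11.
- Rash: 52 terms, including severe named diagnoses.

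**2. Where each kind of case is counted.**

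| How the site records the event | AESI summary (SAP 8.4.1.1) | SOC/PT tables and listings (SAP 8.4.1) | Measured-value thresholds (SAP 8.4.2, Appendix E) |
|---|---|---|---|
| Laboratory term only | Counted | Shown | Counted if a threshold is met |
| Laboratory term and diagnosis | Counted, through the laboratory term | Both shown | Counted if a threshold is met |
| Hepatic-injury diagnosis only | **Not counted** | Shown under its own term | Counted if a threshold is met |

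Only the third row is affected, and only in the first column.

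**3. Illustrative effect on incidence.** With about 108 subjects expected (protocol 12.1), assume 10 have a transaminase event and 1 or 2 of those are recorded only as a diagnosis:
- all counted: 10/108 = 9.3%
- one missed: 9/108 = 8.3%
- two missed: 8/108 = 7.4%

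The counts of 10, 1 and 2 are assumptions. Overall incidence moves little. A row such as serious events would change more in relative terms, but only if the missed subjects happened to be the serious cases.

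**4. Chance that at least one marked event is missed.** Let q be the probability that a marked event is recorded only as a diagnosis, and k the number of such events, treated as independent. Then P(at least one missed) = 1 − (1 − q)^k. For example, with k = 2 and q = 0.25: 1 − 0.75² = 0.438.

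| k | q = 0.10 | q = 0.25 | q = 0.50 | q = 0.75 |
|---|---|---|---|---|
| 1 | 10% | 25% | 50% | 75% |
| 2 | 19% | 44% | 75% | 94% |
| 3 | 27% | 58% | 88% | 98% |

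The documents fix neither q nor k. The table shows only that with a handful of marked events, the summary could be complete or could miss one or more, depending on site practice.

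**The case against.** The strongest reply is that most of this information is reported elsewhere. SAP 8.4.1 tabulates Grade 3/4/5, related, serious and related serious events, and events leading to interruption, discontinuation or death, all by preferred term. It also lists subjects with events leading to discontinuation or interruption, Grade 3/4/5 events, SAEs and deaths. SAP 8.4.2 and Appendix E count subjects by ALT/AST bands and by combined enzyme and bilirubin criteria, whatever the coding. This stands: nothing is lost from the report. What remains is that diagnosed events are not combined with laboratory-term events, and their duration and onset are not summarised.

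A second reply is that the AESI is called elevated transaminases, not liver injury, and the list fits its name. The rash comparison is also inexact, because rash has no parallel measured-value analysis. Both are fair, and a narrow list may be deliberate. The SAP does not say so, however, and does not address the protocol's preference for diagnoses.

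A reader might infer that the gravest events are bound to drop out. The documents do not support that. The recording rule applies when possible and falls back to the laboratory finding. The discontinuation rule in protocol 9.8.1 concerns confirmed rises with no convincing other cause, and these can stay under a listed term.

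A reader might also infer that the serious and discontinuation rows are pushed towards zero because "A laboratory value that is Grade 4 will not automatically be an SAE". That goes too far. The next sentence of protocol 13.1.1.2 makes such a value an SAE when the subject's clinical state points to a life-threatening event. Protocol 13.1.2.1 allows seriousness through hospitalisation or medical importance. Because interruption and discontinuation under 9.8.1 rest largely on enzyme values, laboratory terms can fill those rows too.

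**Conclusion.** The gap is real but limited. A transaminase event recorded only as a hepatic-injury diagnosis is not counted in the SAP 8.4.1.1 summary or in any of its rows. Such events may include some of the more serious ones, because work-up makes a diagnosis more likely; that is a reasonable expectation about site behaviour, not something the documents establish.

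The number affected is unknown. It could be zero if sites keep the laboratory term or record both. The percentages above rest entirely on assumed counts and an assumed recording probability. Safety analysis is descriptive, so no test or inference changes. The point is a low-cost improvement to one grouped summary under the primary objective; it does not show that the safety report would conceal liver events.

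**What to change.** Keep the present 11-term list and its summary unchanged. Add to SAP 8.4.1.1 and Appendix F a second row set, 'elevated transaminases or hepatic-injury diagnosis', with the same categories, duration and time to onset included. Define it by the 11 terms plus a pre-specified list of diagnoses, for example drug-induced liver injury, hepatotoxicity, liver injury, hepatocellular injury and non-infectious hepatitis terms, checked against the MedDRA version in use. Exclude viral hepatitis terms: protocol 9.8.1 cites viral hepatitis as an example of an alternative cause, and including it would blur the row set.

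SAP Section 3 already requires amendments to be approved before database lock, so no new timing rule is needed.

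The cost is one extra term list and one table block, with no new data collection. The broader row set may show a slightly higher count. Presenting both keeps comparability with any summary based on the narrow list, which is why adding rows is preferable to replacing the list.
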